2 PROTOCOL SYNOPSIS

Title	EarGenie assessment of a minimum viable product (MVP): a first in human trial of an fNIRS measure of sound detection and speech discrimination in normal hearing infants
Trial Description	This is a first-in-human clinical trial of EarGenie minimum viable product (MVP).
Objectives	
The primary objective of this trial is to establish the safety and comfort of EarGenie MVP.
 
The secondary objective of this trial is to obtain preliminary evidence that the test results obtained when using EarGenie MVP to test normally-hearing infants are largely consistent with those obtained by a cohort of 36 normally-hearing infants previously tested in our lab with the NIRx NIRScout continuous wave near infrared spectrometer.

Outcomes and Outcome Measures	
The primary outcome is that EarGenie MVP is safe and comfortable for use in human infants. The measure is documentation of any adverse events (safety) or discomfort (e.g., crying, not settling to sleep) shown by the baby when wearing the device.
 
The secondary outcome is that the test results obtained with EarGenie MVP are largely consistent with the sensitivity and specificity of the test results formerly obtained with our NIRx NIRScout research device in normal-hearing infants, thus confirming the suitability of EarGenie MVP for further clinical studies. The outcome measure is the proportion of babies who show a significant detection and discrimination response and also produce fNIRS average waveforms with shape consistent with those shown in the previous studies. To be consistent with the NIRx results we would require not more than 1(/10) baby (or 10%) to have an absent detection response at 65 dB SPL and not more than 3 (/10) babies (or 30%) to show an absent discrimination response for “Ba” versus “Ga”.

Trial Population	Ten infants with normal hearing
Description of sites enrolling participants	This trial will be conducted at the Bionics Institute, [name].
Description of Interventions	
Each infant will have functional near-infrared spectroscopy (fNIRS) performed using EarGenie MVP, to measure changes in cortical blood oxygenation in response to increased neural activity during sound detection and discrimination.
 
During testing, which is performed during natural sleep, the infant wears the custom-made headgear while sounds are presented either through tube-phones or via a loudspeaker.
 
The infant will be presented with different speech sounds at 65 dB SPL. The device runs two automated tests, one to measure whether the baby detected the sound and the other to test whether the

Title: EarGenie minimum viable product (MVP)

Protocol Number: 98058

Version & date: version 3, dated 15 September 2023

Page 5 of 31

	
baby discriminated between two different speech sounds (“Ba” and “Ga”). The sound levels used are not hazardous to the individual.
 
The headgear comprises a soft material headband and a detachable, Bluetooth-enabled, battery-powered montage. The montage is made up of a flexible printed circuit board, flat-surfaced optical LED emitters and detectors and a flexible montage cover.
 
The montage is positioned so that the sensors are located over the regions of the brain that process sound and language. Near infrared light, with 740 nm and 860 nm centre wavelengths, travels from each emitter through the scalp and underlying cortical brain tissues. The detectors measure that portion of the light that is transmitted back to the scalp (the rest being harmlessly absorbed or scattered) and, from these optical measurements, changes in oxygenated and de-oxygenated haemoglobin concentrations are calculated. Changes in these measures that are time locked to the presentation of sound, or a change of sound, provide an index of sound detection and discrimination, respectively.
 
The EarGenie MVP device is controlled using a graphical user interface running on a laptop computer, which allows the user to control sound presentation, visualise optical measurements and obtain the results of our patented, automated response-detection algorithm in real time.

Trial Duration	6 months or until 10 infants have been tested, whichever is shorter
Participant Duration	Infants will have just one test session, which typically takes around 2 hours.

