7 RISK/BENEFIT ASSESSMENT

7.1 Known potential risks

- We do not anticipate any adverse events directly related to the protocol procedures. fNIRS measurements have been safely used in research studies in paediatric populations across the world for many years, and in our laboratory for the past five years, without adverse events. It is a safe technology suitable for use in infants. Other test procedures, such as otoscopy and tympanometry or head circumference measurements, are standard clinical procedures which do not cause discomfort and are not expected to cause distress.
- The EarGenie MVP has been designed by a medical device prototyping company to be safe. It has no mains power attached to any part that is in contact with the infant. The montage contains a 3.7V lithium polymer (LiPo) battery (see Investigator’s Brochure for details), which is not in contact with the infant, and can only be recharged using a dedicated charging cradle (i.e., it is impossible to attempt to charge the battery while on the infant’s head). The headgear communicates to the dedicated computer via Bluetooth. Only the headband and montage cover are in contact with the infant. The headband is made from soft medical grade material (see IB) and the optode montage is covered with a thin flexible single-use cover made from TPU (Thermoplastic Polyurethane), a material commonly used in healthcare applications, with no known aggravation effects. To mitigate cross-infection risk, the montage

covers are designed to be single use, and the headband is wipeable with alcohol wipes or similar after each use.

- Our clinical team is led by an expert paediatric audiologist with over 35 years' experience in infant diagnostics; all testers are either qualified audiologists or trained and directly supervised during testing (at elbow) by qualified audiologists.
- The fNIRS test can only be carried out if the infant is either asleep or quietly being entertained. Testing will be discontinued if the baby becomes distressed and cannot be resettled at any time.

Discomfort or skin damage from headgear

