8.2 Outcomes

Table listing objectives and outcomes.

OBJECTIVE	OUTCOME & OUTCOME MEASURE
Primary	
The primary objective of this trial is to establish the safety and comfort of EarGenie MVP.	The intended outcome is that EarGenie MVP is safe and comfortable for use in human infants. The measure is the incidence of any adverse events recorded (safety) and incidence of discomfort. The measures of discomfort will include observations of crying, attempts to remove headgear, verbal indications of distress (in an infant with developed speech), and observations of any marks left by the headgear on the skin, along with the duration (in minutes) of such incidents. The summary report will be presented as incidence of such events along with their duration, and a full description of each incident.
Secondary	
The secondary objective of this trial is to obtain preliminary evidence of device feasibility by showing that the test results obtained when using EarGenie MVP to test normally-hearing infants are largely consistent with those obtained by a cohort of 36 normally-hearing infants previously tested in our lab with the NIRx NIRScout continuous wave near infrared spectrometer.	The secondary outcome is that the test results obtained with EarGenie MVP are largely consistent with the sensitivity and specificity of the test results formerly obtained with our NIRx NIRScout research device in normal-hearing infants, thus confirming the suitability of EarGenie MVP for further clinical studies. The outcome measure is the proportion of babies who show a significant detection and discrimination response and also produce fNIRS average waveforms with shape consistent with those shown in the previous studies. Specifically, we expect that at least 9/10 infants (90%) will show a significant detection response for “Ba” at 65 dB SPL, and that their average waveforms for

OBJECTIVE	OUTCOME & OUTCOME MEASURE
	
this test should consist of a positive HbO peak around 5-8 s latency, or a negative HbO response with latency 12-16 s, or a shape consistent with a combination of these shapes (refer to Figure 1).
 
For the test of discrimination of “Ba” from “Ga”, we expect that at least 7/10 infants (70%) will show a significant discrimination response, and that their average response waveforms should consist of a positive HbO response with latency 6-12 s or a negative HbO response with latency 12-20 s, or a combination of both these shapes (Figure 2).

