Our outcome measures for device feasibility are the incidence of detection and discrimination responses obtained. Specifically, we expect that at least 9/10 infants (90%) will show a significant detection response for “Ba” at 65 dB SPL, and that their average waveforms for this test should consist of a positive HbO peak around 5-8 s latency, or a negative HbO response with latency 12-16 s, or a shape consistent with a combination of these shapes (refer to Figure 1). For the test of discrimination of “Ba” from “Ga”, we expect that at least 7/10 infants (70%) will show a significant discrimination response, and that their average response waveforms should consist of a positive HbO response with latency 6-12 s or a negative HbO response with latency 12-20 s, or a combination of both these shapes (Figure 2).

During the test session, the infant will be monitored for any signs of discomfort or distress, and after the session. The measures of discomfort will include observations of crying, attempts to remove headgear, verbal indications of distress (in an infant with developed speech), and, after the test, observations of any marks left by the headgear on the skin, along with the duration (in minutes) of such incidents. The infant’s skin will be examined to detect any signs of skin reaction or areas affected by too much pressure of the head gear. If any distress or skin reactions occur in the test session, the parents will be contacted in the following 48 hours to document whether the problem resolved and how long it took. Any comments provided by the parents within 48 hours of the test re any potential side effects noticed will be recorded. All of this information will be documented on the Case Report Form. All Case Report Forms will be collated and summarised in a final report re safety, along with any recorded adverse events.

Adverse events: Since fNIRS tests are considered to be non-invasive and safe, we do not anticipate any serious adverse events. However, if an adverse event occurs, the ethics committee will be informed if required by their procedures, and the standard procedures of the Bionics Institute will be followed (see Section 13).

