16.3 Methods of analysis

Safety analysis: A careful recording during all of the 10 test sessions of any signs of discomfort from the infant, along with any parent reports of such discomfort within 48 hours of the test, will be noted on Case Report Forms and collated and summarised at the end of the study. Any adverse events will be recorded and managed as per Section 13. The data will be presented as incidence of such events along with their duration, and a full description of each incident.

To obtain preliminary evidence of the functionality of the EarGenie MVP, the automatic reports generated by EarGenie MVP, which includes the test result and the average haemodynamic response waveforms related to that test, will be examined. We expect infants with normal hearing to be able to both hear the speech sounds and to be able to discriminate them. Therefore, we expect a majority of infants to return a positive test result (as in our previous research with the NIRx system), and that the waveforms generated should have characteristics in common with what we expect from our previous research. These data will be summarised as proportions of infants for whom the EarGenie MVP test showed a) a significant detection, and b) a significant discrimination as detailed below.

Specifically, we expect that at least 9/10 infants will show a significant detection response for "Ba" at 65 dB SPL, and that their average waveforms for this test should consist of a positive HbO peak around 5-8 s latency, or a negative HbO response with latency 12-16 s, or a shape consistent with a combination of these shapes (refer to Figure 1).

For the test of discrimination of "Ba" from "Ga", we expect that at least 7/10 infants will show a significant discrimination response, and that their average response waveforms should consist of a positive HbO response with latency 6-12 s or a negative HbO response with latency 12-20 s, or a combination of both these shapes (Figure 2).

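### Do the absent-response cut-off in the synopsis and the present-response cut-off in Sections 8.2, 12.3 and 16.3 set different standards for the secondary outcome?

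*Combined protocol and SAP*

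**What the plan says.** The synopsis (Section 2) sets the requirement as a maximum number of absent responses. Its detection limit reads "not more than 1(/10) baby (or 10%) to have an absent detection response at 65 dB SPL". The corresponding limit for the second test, discrimination, reads "not more than 3 (/10) babies (or 30%) to show an absent discrimination response".

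Sections 8.2, 12.3 and 16.3 set it as a minimum number of present responses. For detection, Section 8.2 expects that "at least 9/10 infants (90%) will show a significant detection response". For discrimination, Section 16.3 says "we expect that at least 7/10 infants will show a significant discrimination response".

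The outcome measure itself is worded as presence, with waveform shape attached: "The outcome measure is the proportion of babies who show a significant detection and discrimination response and also produce fNIRS average waveforms with shape consistent". The synopsis uses the same definition just before its cut-off. Section 12.3 puts it more briefly: "Our outcome measures for device feasibility are the incidence of detection and discrimination responses obtained". The analysis section reports "proportions of infants for whom the EarGenie MVP test showed a) a significant detection, and b) a significant discrimination as detailed below", and the paragraphs that follow give the count and the expected waveform together.

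On incomplete data:

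- Section 16.2 analyses every infant in the study.
- Section 16.2.1 marks missing data as not applicable, because withdrawals are replaced.
- Section 12.5.4 allows replacement after withdrawal.
- Section 12.5.5 treats an infant with only part of the fNIRS testing done as having completed the trial.
- Section 7.1 gives a way for a test to end early without withdrawal: "Testing will be discontinued if the baby becomes distressed and cannot be resettled at any time".

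**The concern.** A ceiling on absences and a floor on presences are the same rule only if every infant is one or the other. An infant who wakes early, or who cannot be resettled, may have no result on one test. That infant has not withdrawn, so the replacement rule does not clearly apply, and Section 16.2.1 does not say how the test is counted. Read literally over 10, the synopsis wording does not hold the unfinished test against the device, while the other wording does.

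The synopsis and Section 8.2 tie this outcome to the device's suitability for further clinical studies. With ten infants, one can decide the verdict. If the convention is unstated, it could be chosen once the results are known. A similar doubt arises over waveform: the synopsis cut-off mentions only absent responses, so it is not explicit whether a significant response with an unexpected shape counts.

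**Working it through.** **Inputs.** Ten infants (Section 2). Cut-offs: absent ≤1 and ≤3 (Section 2); present ≥9 and ≥7 (Sections 8.2, 12.3, 16.3). Earlier sensitivities: 97% for detection and 78% for discrimination (Section 6.2), used only for illustration, with infants taken as independent. Section 16.1 gives no power or sample-size figure to reproduce.

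**Complete data.** With x present, absent = 10 − x.

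- Detection: 10 − x ≤ 1 is the same as x ≥ 9.
- Discrimination: 10 − x ≤ 3 is the same as x ≥ 7.

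The wordings agree at all 11 values of x for each test. The chance of meeting the mark is P(X ≥ 9) = 0.97^10 + 10 × 0.97^9 × 0.03 = 0.737 + 0.228 = 0.965 for detection, and P(X ≥ 7) = 0.841 for discrimination.

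**One unfinished test, counts kept over 10.** With x present among 9 completed, absent = 9 − x.

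- Detection: the ceiling is met if x ≥ 8 and the floor if x ≥ 9. They conflict only at x = 8 (8/1/1). P = 9 × 0.97^8 × 0.03 = 0.212.
- Discrimination: the ceiling is met if x ≥ 6 and the floor if x ≥ 7. They conflict only at x = 6 (6/3/1). P = 84 × 0.78^6 × 0.22^3 = 0.201.

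If 97% and 78% are taken to be 35/36 and 28/36, these become 0.200 and 0.204. Over the exact 95% limits of those proportions (0.855–0.999 and 0.608–0.899) they range over 0.006–0.390 and 0.046–0.273. All are conditional on exactly one unfinished test.

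**One unfinished test, percentages of completed tests.** Both wordings give the same answer at every split. At the two splits above, both fail:

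| Test | Present | Mark | Absent | Ceiling |
|---|---|---|---|---|
| Detection | 8/9 = 88.9% | 90% | 1/9 = 11.1% | 10% |
| Discrimination | 6/9 = 66.7% | 70% | 3/9 = 33.3% | 30% |

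This is also the verdict of the floor applied over all ten (8 < 9; 6 < 7). So with one unfinished test, three of the four readings agree everywhere. Only the absence count over 10 stands apart.

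**Two unfinished tests.** With counts over 10, the wordings conflict at 5/3/2 and 6/2/2 for discrimination (probability 0.477), and at 7/1/2 and 8/0/2 for detection (0.978). As percentages of completed tests they still never conflict. Here, however, the denominator itself matters: 8/0/2 is 8/8 = 100% of completed detection tests but 8/10 = 80% of all infants.

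**What Section 16 gives.** Section 16.2 supplies the denominator (all infants) and Section 16.3 the numerator (infants whose test showed a significant response). An unfinished test is not in that numerator. Both borderline splits therefore fall short of the mark.

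**Tympanometry.** Under Section 12.3 a session that ends for abnormal tympanometry in both ears ends before any fNIRS test. Section 12.5.5 requires some fNIRS result for completion and closes the trial at ten tested infants. On that definition such an infant is not one of the ten and cannot create these splits.

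**Waveform.** One off-pattern infant would reverse a result lying exactly on the mark if shape is required. The chance of such a result with complete data is 10 × 0.97^9 × 0.03 = 0.228 at 9/10 and 120 × 0.78^7 × 0.22^3 = 0.224 at 7/10. Section 16.3 joins response and shape in the same sentences, and Section 9.1 reports that shapes did not vary between infants or with age on the earlier device.

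**The case for a change.** The best case for a change is that unfinished tests are foreseen, not hypothetical. Testing depends on natural sleep, partial testing counts as completion, only withdrawals are named as replaceable, and missing data is nonetheless marked not applicable. The study is open and single-arm, so an unwritten convention could be settled after the results are seen. With two unfinished tests the literal wordings conflict often. Aligning the text would cost only a few sentences.

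Much of this stands as description. Section 16.2.1 does not cover a test left unfinished without withdrawal, and the synopsis sentence is worded differently from the rest.

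The conclusion drawn from it does not stand. The conflict needs three things at once: raw counts over 10, the synopsis's own percentages set aside, and an unfinished test treated as neither outcome. No section adopts that reading, and the synopsis defines its measure as a proportion showing a response. The probabilities depend on a number of unfinished tests for which the protocol gives no rate. Section 12.3 plans extra sounds if the infant is still asleep after both main tests, so it contemplates both fitting within one sleep.

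Nor is one alternative convention clearly better. Scoring an unfinished test as a non-response mixes failure to stay asleep with failure to hear, and the documents do not say whether the 97% and 78% were scored that way. Using completed tests avoids this but departs from Section 16.2.

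**Conclusion.** The difference in wording is real but does not call for a change. With complete data it vanishes. With one unfinished test it affects one split in ten per test, with conditional probability about 0.2 at the earlier device's rates, and only under a literal reading of the synopsis. Following Section 16 as written gives a sound descriptive result: significant responses over all infants, set beside the expected 9/10 and 7/10, with waveforms described alongside.

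The outcome is secondary and preliminary, three of the four sections say what is expected and do not require it, and Section 16.1 disclaims formal statistical analysis. No error rate, power figure or safety conclusion rests on it. Any report that lists ten infants' results would show an 8/1/1 or 6/3/1 split, or an off-pattern waveform, for the reader to judge.

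This rests on taking the analysis section as governing over the synopsis and on unfinished tests being few. If two or more infants failed to finish a test, the choice between all infants and completed tests could change the verdict. Section 16.2 then points to all infants.

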3 GLOSSARY OF ABBREVIATIONS

ABBREVIATION	TERM
ADE	Adverse Device Effect
AE	Adverse Event
AR	Adverse Reaction
ASADE	Anticipated Serious Adverse Device Effect
CAPA	Corrective And Preventative Action plan
COI	Conflict of Interest
CRF / eCRF	Case Report Form / electronic Case Report Form
DMC SMC	Data Monitoring Committee / Safety Monitoring Committee
DSMB	Data Safety Monitoring Board
fNIRS	Functional near infrared spectroscopy
GCP	Good Clinical Practice
HREC	Human Research Ethics Committee

IB	Investigator's Brochure
ICH	International Conference on Harmonisation
ID	Identity
IMD	Investigational Medical Device
IMP	Investigational Medicinal Product
ISO	International Organization for Standardization
MedDRA	Medical Dictionary for Regulatory Activities
MSDS	Material Safety Data Sheet
MVP	Minimum Viable Product
PI / CPI	Principal Investigator / Coordinating or Chief Principal Investigator
PICF	Participant Information and Consent Form
QA	Quality Assurance
QC	Quality Control
RCH	Royal Children's Hospital (Melbourne)
RGO	Research Governance Office
SADE	Serious Adverse Device Effect
SAE	Serious Adverse Event
SAR	Serious Adverse Reaction
SMC	Safety Monitoring Committee
SOP	Standard Operating Procedure
SSI	Significant Safety Issue
SUSAR	Suspected Unexpected Serious Adverse Reaction
TGA	Therapeutic Goods Administration
USADE	Unanticipated Serious Adverse Device
USM	Urgent Safety Measure

[figure not shown]

5 ADMINISTRATIVE INFORMATION

5.1 Trial registration

5.1.1 Trial registry

This trial has been registered on ClinicalTrials.gov.

Identifier: NCT05962814

5.3 Expected duration of study

This study will be conducted over 6 months or until 10 infants have been tested, whichever is shorter.

6 INTRODUCTION AND BACKGROUND

6.1 Trial rationale and aim

As part of our ongoing research program (RCH Ethics 71941), and using a research fNIRS device (NIRx NIRScout), we have developed test protocols and signal processing algorithms that can reliably inform whether an infant has detected sounds and whether their brain can distinguish between two different speech sounds (McKay, Wunderlich et al. 2023). We have now developed a clinical investigation device prototype (EarGenie MVP) using the same principles but with hardware and software that is specific for use in audiology clinics. This proposed clinical trial will evaluate the safety and basic functionality of our EarGenie MVP, which has been developed in collaboration with the commercial industrial design house Design + Industry (D+I).

The primary aim of this trial is to establish the safety and comfort of EarGenie MVP.

The secondary aim is to obtain preliminary evidence that the test results obtained when using EarGenie MVP to test normally-hearing infants are largely consistent with those obtained in a cohort of 36 normally-hearing infants previously tested in our lab with the NIRx NIRScout continuous wave near infrared spectrometer, thus confirming the basic functionality of EarGenie MVP.

